Fecal calprotectin	Primary objective 7.2.1.d, Secondary objectives 7.3.1.g and 7.3.1.h.	mg/kg
Plasma CRP	Primary objective 7.2.1.d Secondary objective 7.3.1.t	mg/L
Blood hemoglobin	Primary objective 7.2.1.d, Secondary objective 7.3.1.u	g/L
Blood leukocytes	Primary objective 7.2.1.d Secondary objective 7.3.1.v	cells/L
Blood thrombocytes	Primary objective 7.2.1.d Secondary objective 7.3.1.w	cells/L
Blood lymphocytes	Primary objective 7.2.1.d Secondary objective 7.3.1.x	cells/L
Blood neutrophiles	Primary objective 7.2.1.d Secondary objective 7.3.1.y	cells/L
Plasma albumin	Primary objective 7.2.1.d Secondary objective 7.3.1.z	g/L
Tofacitinib dose	Secondary objectives 7.3.1.a, 7.3.1.aa and 7.3.1.bb	mg*times/per day or "not on treatment"
Colectomies	Secondary objective 7.3.1.cc	Date
Type of healthcare contact	Secondary objective 7.3.1.cc	outpatient visit, remote contact, emergency visit or hospitalization

Variable	Role	Operational definition
Prior IBD treatments	Secondary objective 7.3.2	Yes/no (For each treatment)
 corticosteroids 5-aminosalicylic acid (5-ASA) azathioprine 6-mercaptopurine methotrexate cyclosporine ustekinumab vedolizumab adalimumab infliximab golimumab 		
Concomitant medications o corticosteroids o 5-ASA	Secondary objective 7.3.1.q,	product & dose
Extraintestinal manifestations: arthralgia, arthritis, sacroiliitis, pyoderma gangrenosum, erythema nodosum, primary sclerosing cholangitis, uveitis, ankylosing spondylitis, aphthous stomatitis, psoriasis	CCI	Yes/no per pre-specified list
Prior diagnoses	CCI	Yes/no per pre-specified list
Death date or lost to follow up	Used to define end of follow up	Date

Further operational definitions from the collected data include:

Active disease:

• An endoscopic Mayo sub-score of ≥ 2 or fecal-calprotectin (f-calpro) > 250 mg/kg.

Clinical response:

• A full Mayo score decrease of ≥ 3 points and a decrease of $\geq 30\%$ from baseline, with a decrease of ≥ 1 point on the rectal bleeding subscore or an absolute rectal bleeding score of ≤ 1 .

• A partial Mayo score (ie, Mayo score without endoscopic assessment) decrease of ≥2 points and reduction of at least 25% in partial Mayo (pMayo) score from baseline with an accompanying decrease in rectal bleeding sub score of ≥1 point or absolute rectal bleeding sub score of ≤1.

Clinical remission:

- A full Mayo score of ≤ 2 points with no individual sub score exceeding 1 point, with rectal bleeding sub-score of 0.

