6 HANDLING OF MISSING VALUES

No imputation for missing values will be performed. Proportion of missing values will be reported where appropriate.

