7 STATISTICAL METHODOLOGY AND STATISTICAL ANALYSES

7.1 STATISTICAL METHODS

General:

Means, medians, and standard deviations, and 25% and 75% quartiles will be provided for continuous variables when performing descriptive analysis of continuous data. Numbers and percentages will be provided for dichotomous and polychotomous variables when performing descriptive analysis of categorical data.

Serial measures collected will be handled by "carry forward imputation", i.e. the latest value will be assumed unchanged until otherwise proven. Thus for each timepoint, the latest available measure will be used. Patients will be censored from the study post the last available contact/data entry. Missing values will not be imputed.

An unadjusted Kaplan Meier curve will be drawn to illustrate time-to-event and to estimate medians for time-to-event outcomes.

All data analysis will be executed using R, a language and environment for statistical computing and graphics, version 4.0.3 or later in Rstudio environment.

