7.2 STATISTICAL ANALYSES

Primary objectives a-e:

Describe the patient population at the baseline (initiation of tofacitinib), using the data collected. For each continuous variables (age, BMI, age at diagnosis, duration of disease, laboratory measures), provide the mean, median, sd, 25%Q and 75%Q values. For categorical variables (sex, smoking status, extent of colonic involvement, disease severity, endoscopic findings), report the number of patients, and proportion. Report proportion of missing values if present.

Secondary objective - Assess the Real-world Effectiveness of Tofacitinib

Secondary objective a:

For each patient, define the "on treatment" as Yes/No based on the latest available dose (at each timepoint 8, 16, 24 and 52 weeks). Patients marked with "not on treatment" prior to timepoint will be regarded as discontinued.

Report the proportion of patients on treatment, not censored at each timepoint.

Secondary objectives b, c, d, e, g, n:

For each patient, define the fulfilment of the remission/response criteria as Yes/No based on the latest available data (at each timepoint 8, 16, 24 and 52 weeks).

Report the proportion of patients on fulfilling the response/remission criteria, not censored at each timepoint.

Secondary objective f:

Define the time of response for each patient as first ever data-entry that fulfils response criteria. Fit competing-risk time-to-event model to the data, with time-to-event defined as time from index until response (event) or discontinuation (competing event), or end of data collection (censoring event).

Assess the cumulative incidence as function of time for both types of events. Illustrate the Aalen-Johansen state probabilities of multistate model.

Secondary objective h:

Select only patients with baseline f-calprotectin above 250 mg/kg at baseline. For each subsequent f-calprotectin measure, define below 250 mg/kg as Yes/No variable. Additionally, estimate the absolute delta change per baseline value.

For each timepoint (week 8, 16, 24 and 52), report the proportion of patients on fulfilling the <250mg/kg criteria, and summary statistics (mean, median, sd, 25%Q and 75%Q) of delta change, among patients not censored at each timepoint.

Secondary objectives i, j, k, m, o:

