For each subsequent visit, define the higher (10mg) dosing as Yes/No variable. For each timepoint (week 8, 16, 24 and 52), report the proportion of patients, among patients not censored at each timepoint.

Secondary objective cc:

Create composite endpoint of drug discontinuation, colectomy or UC-hospitalization, with time of the event as earliest of the aforementioned. Analyse time to event using Kaplan-Meier fit, where time to event is defined as time from index until composite endpoint (event) or time of data collection (censoring event).

Plot the Kaplan-Meier fit with the 95% CI and report the median survival if reached.

Secondary objective - Assess Treatment Lines Prior to Tofacitinib Treatment

Secondary objective a:

Summarize and tabulate types of previous UC treatments. Report N and proportion of patients that had corresponding treatment recorded.

Report the summary statistics (mean, median, sd, 25%Q and 75%Q) of number of treatments prior to tofacitinib if feasible.

NA

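### Weekly effectiveness rates use only patients whose chart continues to that week, which merges too-recent starters with patients who left the chart and conflicts with the censoring used for objectives f and cc

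*SAP*

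**What the plan says.** SAP 7.1 sets the general censoring rule: "Patients will be censored from the study post the last available contact/data entry". It also sets a carry-forward rule: "Thus for each timepoint, the latest available measure will be used". SAP 6 adds: "No imputation for missing values will be performed. Proportion of missing values will be reported where appropriate".

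SAP 7.2 then restricts the reported rates. For objectives b, c, d, e, g and n it says: "Report the proportion of patients on fulfilling the response/remission criteria, not censored at each timepoint". The same restriction to uncensored patients appears for a, h, i to m, o, q to z and bb, and it reaches p through b and c.

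Discontinuation has a rule under objective a, "Patients marked with 'not on treatment' prior to timepoint will be regarded as discontinued", but no rule under b to e, g or n.

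Two objectives follow a different scheme. In f, a patient leaves the risk set through response, "discontinuation (competing event), or end of data collection (censoring event"). In cc, the time runs as "time from index until composite endpoint (event) or time of data collection (censoring event"). SAP Table 1 also lists a date of death or loss to follow-up, described as "Used to define end of follow up", but no analysis in 7.2 says how it is used.

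**The concern.** Read together, 7.1 and 7.2 let the last chart entry decide who is counted at each week. Two kinds of patient are removed by the same rule. One started tofacitinib too recently for the week to have been reached when the data were collected; leaving that patient out is proper. The other could have reached the week but has no later entry, and that absence may be related to how the patient was doing.

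The remission, response and marker rates at weeks 16 to 52 are therefore conditional on still generating chart entries. The composition of the denominator also changes from week to week for reasons the report would not show, so a reader could not tell a change in disease from a change in who is observed. In a single-cohort descriptive study these proportions are the effectiveness result.

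The plan also treats the same patient in different ways. A recorded stop can drop out of the weekly rates while it remains an event in cc.

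**Working it through.** **1. One patient under each rule.** Take a patient recorded as not on treatment at week 10, with no response before that, no entry after week 20, and an index date early enough for week 52 to have been reached.

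| Objective | Treatment under the SAP |
|---|---|
| a, weeks 24 and 52 | Regarded as discontinued, but the reported proportion is restricted to uncensored patients, so read literally the patient is not counted |
| b to e, weeks 24 and 52 | Not in the denominator |
| f | Competing event at week 10 |
| cc | Event at week 10 (or earlier, if another component came first) |

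Carry-forward does not bring this patient back: censoring starts after the last entry, so no value is carried to week 24 or 52.

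**2. Eligibility can be known from dates alone.** Protocol section 5 plans data collection from 01 December 2021 to 30 May 2022. Fifty-two weeks is 364 days. Week 52 is reachable for index dates up to 02 December 2020 if the chart is read on the first of those dates, and up to 31 May 2021 if it is read on the last. A denominator that does not depend on contact can therefore be computed.

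**3. How far the rate can move.** The plan gives no expected rate or loss rate, so there is no figure of its own to reproduce. The inputs below are assumptions:

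- p: share of eligible patients who would meet the criterion at the week if all had an entry there
- f: share of those not meeting it whose last entry is earlier
- r: share of those meeting it whose last entry is earlier

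Reported rate = p(1 − r) / [p(1 − r) + (1 − p)(1 − f)].

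Per 100 eligible patients, with p = 40%:

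| f | r | Reported rate | Shift (points) | Lost | Bounds, all 100 in base |
|---|---|---|---|---|---|
| 30% | 0 | 40/82 = 48.8% | +8.8 | 18 | 40% to 58% |
| 20% | 20% | 32/80 = 40.0% | 0 | 20 | 32% to 52% |
| 10% | 30% | 28/82 = 34.1% | −5.9 | 18 | 28% to 46% |
| 0 | 30% | 28/88 = 31.8% | −8.2 | 12 | 28% to 40% |

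The lower bound counts every lost patient as not meeting the criterion; the upper bound counts every one as meeting it. The true 40% lies within the bounds in each row. With f = 30% and r = 0, a true 30% becomes 30/79 = 38.0% and a true 50% becomes 50/85 = 58.8%. The percentages do not depend on whether N is 100 or 150.

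**4. What the report would show.** The Table 3 shell gives N at each week. N falls both for late starters and for patients who left, and nothing in the shell separates them. A censored patient is outside the denominator and so need not appear in the missing-value proportion, which is in any case given only where appropriate.

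**The case against.** The strongest reply has four parts.

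- **Role of the endpoints.** The primary objective is baseline description. The affected endpoints are secondary and descriptive, and no test or sample size depends on them. This stands, and it limits the severity.
- **Existing handling.** Table 3 shows N per week, discontinuation is reported in a, f and cc, and protocol 8.9 admits incomplete data. This stands as partial mitigation, but none of it separates patients not yet eligible from patients lost. A failing patient with any later entry, including a remote contact, emergency visit or hospital stay, stays in the denominator, so the effect is confined to those who leave the chart.
- **Estimand.** A reader might infer that a patient who stopped and left is a known failure wrongly discarded. The documents do not support that. Clinical remission and response are defined by Mayo scores with no requirement to be on drug, so that patient's later status is unknown. Counting stoppers as failures is a choice to be declared. It has no basis for f-calprotectin, histology or laboratory values, which stopping does not determine.
- **Incomplete repair.** Counting stoppers as failures and merely showing continuing patients without an entry as missing would leave the loss of stable patients uncorrected. This stands, and the fix has to deal with both groups.

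**Conclusion.** The concern holds as a should-fix. As written, the rates at weeks 16 to 52 for nearly all effectiveness objectives depend on contact behaviour, and the censoring rule in 7.1 is not reconciled with the one in f and cc. Under objective a, the literal wording can drop a patient already recorded as off treatment.

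Two stronger readings should be resisted. A reader might infer that the plan overstates effectiveness; the direction is not fixed, and the illustration runs from −8.2 to +8.8 points around 40%. A reader might also count the patients whose start is too recent for week 52 as part of the harm; leaving them out is legitimate, and a denominator based on dates would leave them out too. The fault is only that they cannot be told apart from patients who were lost.

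The real size is unknown. The values of p, f and r are assumptions, and the calendar limits assume the planned collection dates are kept.

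**What to change.** Settle the following in SAP 7.1 and 7.2 before analysis:

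1. **Denominator.** At each week, include all patients whose index date plus that many weeks falls on or before the data-collection date. Table 1 lists no such date, so record it if it is not already captured. Use the same date to reconcile 7.1 with the censoring in f and cc.
2. **Objective a.** Keep recorded discontinuations in the denominator as not on treatment.
3. **Objectives b to e.** As the main row, report the proportion in remission or response while on tofacitinib, with recorded stoppers counted as not meeting it. Label this a composite estimand, not a known Mayo status, and word SAP 6 so that it does not appear to forbid it.
4. **Objectives g, h, n and t to z.** Do not apply the stopper rule. Show the number with no value.
5. **Still on drug at last contact, no entry at the week.** Show the number. Give the rate with the last value carried forward, together with lower and upper bounds.
6. **Table 3.** At each week add N not yet eligible, N stopped and N without later contact.
7. **Sensitivity analysis.** Keep the present rule, restricted to uncensored patients.

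The cost is some SAP wording, possibly one extra date in the data collection tool, a few table rows and a little more analysis. The reported rates may move in either direction.

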#### 7.3. Secondary objectives

#### 7.3.1. To Assess the Real-world Effectiveness of Tofacitinib.

- a. Proportion of patients who are taking to facitinib at week 8, 16, 24 and 52.
- b. To assess rates of clinical remission defined by a full or partial Mayo score at week 8, 16, 24 and 52.
- c. To assess rates of clinical response defined by a full or partial Mayo score at week 8, 16, 24 and 52.
- d. Proportion of patients in steroid-free clinical remission at weeks 8, 16, 24, and 52 as defined by full or partial Mayo who did not require any corticosteroid treatment during the period ≥4 weeks prior to the visit (for all patients and for those treated with corticosteroids at baseline).
- e. Proportion of patients reaching clinical response as defined by full or partial Mayo score at week 8, 16, 24 and 52.

- f. Time to response as assessed by a decrease as defined by full or partial Mayo score.
- g. Proportion of responders defined by a f-calpro reduction of  $\geq 50\%$ ,  $\geq 75\%$  or  $\geq 90\%$  at week 8, 16, 24 and 52 compared to baseline.
- h. Proportion of patients reaching f-calpro below 250 mg/kg at week 8, 16, 24 and 52 of those that had f-calprotectin above 250 mg/kg at baseline and change from baseline in f-calpro at week 8, 16, 24 and 52.
- i. Proportion of patients in sustained remission (pMayo and full Mayo score) from week 8 to week 16, 24 and 52.
- j. Proportion of patients in sustained remission (pMayo and full Mayo score) from week 16 to week 24 and 52.
- k. Proportion of patients in sustained steroid free remission (pMayo and full Mayo score) at week 16 to 24 and 52 (for all patients and for those treated with corticosteroids at baseline).
- 1. Change in partial and full Mayo score at weeks 8/16/24/52.
- m. Proportion of patients in sustained endoscopic remission (sub score = 0), mucosal healing (sub score 0-1) or endoscopic response (sub score reduction from baseline of ≥1) from week 8 to week 16, 24 and 52.
- n. Proportion of patients in physician assessed histological remission determined as inactive disease, or normal histology, and change from baseline in histology assessment (0= normal histology, 1= inactive disease and 2 = active disease) at week 8/16/24/52.

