2.1 STUDY DESIGN

The target population for this study is adult ulcerative colitis patients who were prescribed to facitinib. Estimated number of patients in this study is 100-150, with the aim of covering all ulcerative colitis patients in Finland treated with to facitinib. The main inclusion criteria are a diagnosis of ulcerative colitis (ICD-10: K51) between January 2010 and December 2021 and treatment with to facitinib. The main exclusion criteria are age under 18 years, use of to facitinib before national reimbursement decision on 01 March 2019 and history of panproctocolectomy, ileal pouch-anal anastomosis (IPAA) or ileostomy.

The data collected has been generated as part of standard clinical care, treatment, and follow-up of ulcerative colitis patients. In accordance with the Finnish Act on Secondary Use of Health and Social Data 552/2019 (in Finnish: Laki sosiaali- ja terveystietojen toissijaisesta käytöstä), health registry data can be processed in scientific studies without patient consent. The purpose of this act is to establish conditions for the effective and secure processing of, and access to, personal health and social data for certain secondary purposes, such as research and statistics, innovation and development, knowledge management, teaching and authority planning. Thus, the Secondary Act creates a clear legal basis for the use of such registered data for research and innovation related to, for example, the health and well-being of citizens, the prevention of disease and the development of new treatment methods. This relatively new legislation is also a welcome unification of the fragmented Finnish national rules regarding the use of healthcare and social welfare data. In addition, it takes into consideration current data protection requirements.

The data will be collected by data miners in all hospital districts across Finland and entered into an electronic data mining tool (eDMT) which will be designed for the study in collaboration with Finnish clinicians. The data will be used to investigate and describe the patient population, treatment strategies and disease development.

Figure 1. Study Timeline

FPFV= First patient first visit, LPLV= Last patient last visit.

Please note that dates are subject to change depending on how long permit process with Findata takes.

Study population

The study is a descriptive single cohort study. Patients must meet all of the following inclusion criteria to be eligible for inclusion in the study:

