- h. Proportion of patients reaching f-calpro below 250 mg/kg at week 8, 16, 24 and 52 of those that had f-calprotectin above 250 mg/kg at baseline and change from baseline in f-calpro at week 8, 16, 24 and 52.
- i. Proportion of patients in sustained remission (pMayo and full Mayo score) from week 8 to week 16, 24 and 52.
- j. Proportion of patients in sustained remission (pMayo and full Mayo score) from week 16 to week 24 and 52.

[figure not shown]
k. Proportion of patients in sustained steroid free remission (pMayo and full Mayo score) at week 16 to 24 and 52 (for all patients and for those treated with corticosteroids at baseline).

- *l.* Change in partial and full Mayo score at weeks 8/16/24/52.
- m. Proportion of patients in sustained endoscopic remission (sub score = 0), mucosal healing (sub score 0-1) or endoscopic response (sub score reduction from baseline of ≥ 1) from week 8 to week 16, 24 and 52.
- n. Proportion of patients in physician assessed histological remission determined as inactive disease, or normal histology, and change from baseline in histology assessment (0= normal histology, I= inactive disease and 2 = active disease) at week 8/16/24/52.
- o. Proportion of patients in sustained steroid free remission (pMayo and full Mayo score) (for all patients and for those treated with corticosteroids at baseline) and endoscopic remission (sub score = 0), mucosal healing (sub score 0-1) or endoscopic response (sub score reduction from baseline of ≥ 1) from week 8 to week 16, 24 and 52.
- p. Comparison of response and remission (pMayo and full Mayo score) based on the extent of colonic involvement.
- q. Proportion of patients with corticosteroid tapering at weeks 8/16/24/52 and their tapering rates and doses.
 - note after further discussions, the data required for objective q might not be present in the available medical records and/or prescriptions
- r. Proportion of patients with improvement in stool frequency sub score of 1 or more points and change from baseline in stool frequency sub score at week 8, 16, 24 and 52.
- s. Proportion of patients with improvement in rectal bleeding subscore of 1 or more points and change from baseline in rectal bleeding subscore at week 8, 16, 24 and 52.
- t. Proportion of patients reaching normal P-CRP levels (below 4mg/L) and change from baseline in P-CRP levels at week 8/16/24/52.

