Select only patients that were on remission/steroid free remission at the timepoints. For each patient, define the fulfilment of the remission/response criteria as Yes/No based on the latest available data (at each timepoint 16, 24 and 52 weeks). Report the proportion of patients on fulfilling the remission criteria, not censored at each timepoint.

Secondary objective l:

For each available Mayo score (full or partial), estimate the absolute delta change from baseline value. For each timepoint (week 8, 16, 24 and 52), report the summary statistics (mean, median, sd, 25%Q and 75%Q) of delta change, among patients not censored at each timepoint.

Secondary objective p:

Perform analyses described in secondary objective b and c, stratified by the extent of colonic involvement

Secondary objective q:

For each patient, define the corticosteroid tapering as Yes/No based on the latest available data (at each timepoint 8, 16, 24 and 52 weeks). Additionally, define the tapering rates and doses based on latest available data.

For each timepoint (week 8, 16, 24 and 52), report the proportion of patients that had corticosteroid tapered, among patients not censored at each timepoint. Additionally,

report summary statistics (mean, median, sd, 25%Q and 75%Q) of tapering rates and doses among patients that had corticosteroids tapered.

Secondary objectives r and s:

For each patient, define the fulfilment of the improvement criteria as Yes/No based on the latest available data (at each timepoint 8, 16, 24 and 52 weeks). Additionally, estimate the absolute delta change per baseline value

Report the proportion of patients on fulfilling the response/remission criteria, report the summary statistics (mean, median, sd, 25%Q and 75%Q) of delta change, among patients not censored at each timepoint.

Secondary objectives t-z:

For each subsequent laboratory measure, define "normal-level" as Yes/No variable. Additionally, estimate the absolute delta change per baseline value. For each timepoint (week 8, 16, 24 and 52), report the proportion of patients on fulfilling the "normal-level" criteria and summary statistics (mean, median, sd, 25%Q and 75%Q) of delta change, among patients not censored at each timepoint.

Secondary objective aa:

Report the proportion of patients that received extended induction

Secondary objective bb:

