8 TABLE SHELLS

Table 2: Table shell for patient characteristics for primary objective

				n	missing
Variable	categories	mean (sd)	Median (25Q-75Q)	(%)	%
age				-	
sex	male	-	-		
	female	-	-		
weight				-	
height				-	
(BMI)				-	
smoking	current	-	-		
	ex-smoker	-	-		
	non-smoker	-	-		
age at UC diagnosis				-	
duration of UC				-	
Montreal classification	E1	-	-		
	E2	-	-		
	E3	-	-		
Mayo-score				-	
F-calpro				-	
P-CRP				-	
B-thromb				-	
P-alb				-	
B-leuk				-	
B-ly				-	
B-neutr				-	
B-hb				-	
Endoscopic findings	yes	-	-		
	no	-	-		

Table 3: Table shell for outcome objectives

Objective	Outcome	Week 8	Week 16	week 24	week 52
1	N patients	N	N	N	N
P1 - a	Proportion of patients on treatment	n (%)	n (%)	n (%)	n (%)
P1 - b	Proportion of patients with clinical remission (full Mayo)	n (%)	n (%)	n (%)	n (%)
P1 - b	Proportion of patients with clinical remission (partial Mayo)	n (%)	n (%)	n (%)	n (%)
P1 - c	Proportion of patients with clinical response (partial Mayo)	n (%)	n (%)	n (%)	n (%)
P1 - c	Proportion of patients with clinical response (full Mayo)	n (%)	n (%)	n (%)	n (%)
P1 - d	Proportion of patients with steroid free clinical remission	n (%)	n (%)	n (%)	n (%)
P1 - g	Proportion of patients with f-calpro reduction ≥50%	n (%)	n (%)	n (%)	n (%)
P1 - g	Proportion of patients with f-calpro reduction ≥75%	n (%)	n (%)	n (%)	n (%)
P1 - g	Proportion of patients with f-calpro reduction ≥90%	n (%)	n (%)	n (%)	n (%)
P1 - h	Proportion of patients reaching f-calpro below 250 mg/kg, of those that had f-calprotectin above 250 mg/kg at baseline	n (%)	n (%)	n (%)	n (%)
P1 - h	Change in f-calpro, among patients with f-calprotectin above 250 mg/kg at baseline	Δ -from baseline (mean ± sd)	Δ-from baseline (mean ± sd)	Δ-from baseline (mean ± sd)	Δ-from baseline (mean ± sd)

Objective	Outcome	Week 8	Week 16	week 24	week 52
P1 - i	Proportion of patients in sustained remission (pMayo) from week 8	-	n (%)	n (%)	n (%)
P1 - i	Proportion of patients in sustained remission (full Mayo score) from week 8	-	n (%)	n (%)	n (%)
P1 - j	Proportion of patients in sustained remission (pMayo) from week 16	-	-	n (%)	n (%)
P1 - j	Proportion of patients in sustained remission (full Mayo score) from week 16	-	-	n (%)	n (%)
P1 - k	Proportion of patients in sustained steroid free remission (pMayo) from week 16	-	-	n (%)	n (%)
P1 - k	Proportion of patients in sustained steroid free remission (full Mayo score) from week 16	-	-	n (%)	n (%)

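### SAP 7.2 computes sustained remission only among patients already in remission, but the objectives and Table 3 label it a proportion of patients, and no start week is named

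*SAP*

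**What the plan says.** Protocol 7.3.1, repeated in SAP 2.2, words objective i as "Proportion of patients in sustained remission (pMayo and full Mayo score) from week 8 to week 16, 24 and 52". Objective j has the same form from week 16. Objectives k and o concern steroid-free remission and add that they are wanted "for all patients and for those treated with corticosteroids at baseline". None of these, nor the endpoint list in SAP 5.1, restricts the population to patients in remission.

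The method in SAP 7.2 covers i, j, k, m and o together. Its first step is "Select only patients that were on remission/steroid free remission at the timepoints". It then classifies each patient at weeks 16, 24 and 52 and ends: "Report the proportion of patients on fulfilling the remission criteria, not censored at each timepoint".

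In SAP section 8, the Table 3 row for objective i is labelled "Proportion of patients in sustained remission (pMayo) from week 8", with n (%) in each cell. The rows for j, k, m and o follow the same pattern. The table has one row of N, with a value for each week, and no row for the number in remission at the start week. By contrast, the rows for objective h state their subset: "of those that had f-calprotectin above 250 mg/kg at baseline".

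**The concern.** The quantity computed and the quantity named have different denominators. A reader of Table 3 will take the sustained-remission percentage as the share of tofacitinib patients who were in remission at week 8 (or 16) and stayed there. The SAP rule instead gives the share of those remitters who stayed there, leaving out everyone not in remission at the start week. Both are useful, but they answer different questions, and the second is the larger unless every patient is in remission at the start.

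These rows are the study's evidence on durability of effect. Printed as planned, they would sit beside the remission rows for objective b, which use all uncensored patients, under the same kind of label but on a different base. Two further gaps are in the same paragraph of the SAP: the week at which remission is required is not named, and objective m is selected on remission although its outcomes are endoscopic.

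**Working it through.** The documents give no expected remission rate and no sample-size calculation, so there is no planned figure to reproduce. The check is algebra plus an assumed range.

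**Definitions.** Among patients not censored at the later week, let N = all patients, R = those in remission at the start week, and S = those in remission at the start week and still in remission at the later week.

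- SAP 7.2 figure = S/R.
- All-patient figure = S/N.
- Ratio = (S/R) ÷ (S/N) = N/R = 1/(share in remission at the start week). It does not depend on S.

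**Size over assumed start-week remission rates.**

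| Assumed share in remission at start week | Factor |
|---|---|
| 15% | 1/0.15 = 6.7 |
| 20% | 1/0.20 = 5.0 |
| 25% | 1/0.25 = 4.0 |
| one third | 3.0 |
| 40% | 1/0.40 = 2.5 |
| 50% | 1/0.50 = 2.0 |
| 70% | 1/0.70 = 1.4 |

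The planned cohort size ("Estimated number of patients in this study is 100-150") does not change the factor, apart from rounding of counts. Full Mayo, partial Mayo and steroid-free remission would each have their own start-week share, and so their own factor.

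**Illustration (assumed counts).** N = 120, R = 40, S = 30. SAP 7.2 prints 30/40 = 75.0% (Wilson 95% CI 59.8 to 85.8). The all-patient figure is 30/120 = 25.0% (18.1 to 33.4).

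**Consistency with objective b.** Suppose 12 other patients are also in remission at week 52. Objective b then prints (30 + 12)/120 = 35%, while the sustained row prints 75%. On a common denominator, sustained remission at week 52 is a subset of remission at week 52 and cannot exceed it.

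**Unequal censoring.** Start from 120 patients with 40 remitters and 80 non-remitters.

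- 20% of remitters and 40% of non-remitters censored: R = 32, N = 32 + 48 = 80, factor 80/32 = 2.5.
- The reverse: R = 24, N = 24 + 64 = 88, factor 88/24 = 3.7.
- Equal censoring leaves it at 3.0.

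**The start week.** The selection sentence refers only to the timepoints, and the weeks named next are the assessed ones: 16, 24 and 52. If patients are selected for being in remission at the week being assessed, then all of them meet the criterion at that week, and the result is 100%. The objectives and Table 3 point to week 8 for i, m and o and week 16 for j and k, but 7.2 does not say so.

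**Objective m.** Its outcomes are endoscopic remission, mucosal healing and endoscopic response. Selection on remission or steroid-free remission does not identify the patients who met each of these endoscopic criteria at week 8.

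**The case against.** The restriction is written openly in the SAP, and Protocol 8.7 allows the SAP to modify the protocol's plans. Retention among remitters is a legitimate quantity, and sustained remission from week 8 can be read as already conditional on remission at week 8. Objectives i and j never say all patients. In k and o that phrase partly just contrasts the cohort with the corticosteroid subgroup, as it does in objective d. So the wording favours the all-patient reading without settling it.

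Table 3 also gives a reader some help. Its N is a weekly figure, not one whole-cohort number; the objective h rows already use a subset under it; and n together with % reveals the denominator. That help is partial: Protocol 8.6 prevents export of groups under 5, and gaps in the data may make row denominators differ from N.

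The all-patient figure has its own limit. It counts patients who first reach remission after the start week as not sustained, so it does not measure everyone who ever reaches and keeps remission.

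These points stand, and they make the defect one of an undisclosed and mismatched denominator, not of a wrong formula. They do not remove it. Where the plan intends a subset, as in objective h, it says so in the objective, the method and the table. For i, j, k, m and o only the method does, and the SAP adds no note there, although it annotates b, c, e and q.

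**Conclusion.** The point holds. As written, SAP 7.2 would print retention among remitters under a label that reads as a proportion of all patients. With similar censoring in both groups the printed figure is larger by 1/(start-week remission share): 6.7 to 1.4 for assumed shares of 15% to 70%. It can exceed the remission proportion in objective b at the same week. The unnamed start week is a second defect in the same sentence, because one literal reading makes the result 100%.

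A reader might infer a roughly threefold overstatement. The documents do not support a single factor: three applies only if about one third are in remission at the start week, and no rate is given. A reader might also infer that the rule drops only patients who never reach remission; it drops everyone not in remission at the start week, including later remitters.

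The affected outcomes are secondary and descriptive, with no hypothesis tested. The primary objective, patient characterisation, is untouched. The change should still be made before analysis, because these rows carry the durability findings.

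**What to change.** In SAP 7.2, name the start week: week 8 for i, m and o; week 16 for j and k.

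For i, j, k and o, print two labelled rows in Table 3 at each later week:

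1. Sustained remission, all patients: those in remission at the start week and sustained, divided by all patients not censored at that later week. For k and o, give this also within the baseline-corticosteroid subgroup. Use this row to answer the objective as worded.
2. Retention among patients in remission at the start week, with that number shown as the denominator.

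For m, select and report on the endoscopic criterion itself, with the same two denominators.

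The cost is SAP wording and extra table rows; no new data are needed. The downside is a longer table and a smaller all-patient figure.
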